2.0 OBJECTIVES

2.1 Primary Objective

To determine whether patient-specific mutations correlate with clinical overall response to decitabine in patients with AML or MDS.

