5.0 INVESTIGATIONAL PLAN

5.1 Summary of Study Design

This is an open-label, single-arm, Phase II, biomarker study of patients with AML or MDS who are treated with 10 consecutive days of decitabine. FAB-M3 AML is excluded from this trial, because other well-tolerated options exist for the treatment of FAB-M3 acute promyelocytic leukemia. AML patients who are < 60 years old and have not received cytotoxic induction chemotherapy are also excluded, because cytotoxic therapy offers a curative possibility for these patients. MDS patients without cytopenias are also excluded because these patients can be followed with watchful-waiting.

All patients will undergo bone marrow biopsies pre-study, on Cycle 1 Day 10 \pm 1, and on Day 28 \pm 4 of Cycles 1, 2, 4, and 6. Following Cycle 6, bone marrow biopsies should be performed at the discretion of the treating physician to assess for relapse or progression. Patients will provide a skin biopsy sample pre-study. See Section 8.0 for details on correlative studies.

Patients will receive decitabine 20 mg/m²/day as a 1-hour infusion on consecutive Days 1-10 in 28-day cycles. The dose will be calculated based on actual patient weight at the beginning of each cycle.

Once AML patients achieve morphologic complete remission with incomplete blood count recovery (CRi) or MDS patients achieve a marrow complete response (Marrow CR) as defined in Section 9.0, decitabine administration may be decreased to 20 mg/m²/day for ten consecutive days every 6 weeks, to limit myelosuppressive toxicity and improve count recovery. After 2 cycles at 6 week intervals, the dose may be reduce to 20 mg/m²/day for five consecutive days in 6 week cycles, at the discretion of the treating physician. After two cycles of five consecutive days of treatment, if the patient meets the definition of CR with complete cytogenetic response as defined in Section 9.0, administration may further be decreased to three consecutive days per cycle at the discretion of the treating physician.

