9.1 Response Criteria - AML

AML Patients will be assessed for response according to the IWG criteria:¹

Morphologic complete remission (CR) – Defined as morphologic leukemia-free state, defined as less than 5% blasts in aspirate with marrow spicules and a count of ≥ 200 nucleated cells and no blasts with Auer rods or any persistence of extramedullary disease. When erythroid precursors constitute less than 50% of bone marrow nucleated cells, the percentage of blasts is based on all nucleated cells; when there are 50% or more erythroid cells, the percentage blasts should be based on the nonerythroid cells. The presence of mild megaloblastoid changes may be permitted if they are thought to be consistent with treatment effect. However, persistence of pretreatment abnormalities (eg, pseudo-Pelger-Huet cells, ringed sideroblasts, dysplastic megakaryocytes) are not consistent with CR. In addition, ANC $> 1000/\mu\text{l}$ and platelet count of $\geq 100,000/\mu\text{l}$. Patient must be independent of transfusions. No duration requirement for this designation.

Cytogenetic complete remission (CCR) – Defined as morphologic complete remission plus a reversion to a normal karyotype. For this study, reversion of a normal karyotype is defined as no clonal abnormalities detected in a minimum of 20 mitotic cells.

Morphologic complete remission with incomplete blood count recovery (CRi) – Defined as morphologic complete recovery with the exception of neutropenia $< 1000/\mu\text{l}$ or thrombocytopenia $< 100,000/\mu\text{l}$.

Partial remission (PR) – Defined as meeting the above criteria for complete remission, with the following exceptions: decrease of $\geq 50\%$ in the percentage of blast to 5-25% in the bone marrow aspirate. A value of $\leq 5\%$ blasts in bone marrow with Auer rods present may also be considered a partial remission.

Stable Disease (SD) – Defined as not meeting the definitions of CR, CRi, PR, PD, or recurrence/morphologic relapse.

Progressive disease (PD) – Defined as a clear increase in bone marrow blast count, typically a greater than 50% increase compared with baseline, or new extramedullary disease. Patients with a $> 50\%$ increase in peripheral blast count with an increase of the total peripheral white blood cell count to $> 10,000/\mu\text{l}$ should undergo evaluation by bone marrow biopsy to access for progressive disease.

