9.2 Response Criteria - MDS

MDS Patients will be assessed for response according to the IWG criteria:⁶⁹

Complete remission (CR) – Defined as $\leq 5\%$ myeloblasts with normal maturation of all cell lines in the bone marrow and peripheral blood values of Hgb ≥ 11 g/dL, Platelets $\geq 100 \times 10^9/L$, Neutrophils $\geq 1.0 \times 10^9/L$, and 0% blasts. Persistent dysplasia does not exclude CR but will be noted.

Marrow Complete Response (Marrow CR) – Defined as $\leq 5\%$ myeloblasts in the bone marrow and a decrease by $\geq 50\%$ from pretreatment values, but not meeting the definition of CR above.

Partial Remission (PR) – Defined as meeting the definition of CR above with a decrease of myeloblasts in the bone marrow by $\geq 50\%$ from pretreatment values, but absolute myeloblasts still $>5\%$.

Stable Disease (SD) – Defined as not meeting the definitions of CR, Marrow CR, PR, SD, PD, or recurrence/morphologic relapse.

Progressive Disease//Relapse (PD) – Defined as $\geq 50\%$ increase in blasts to $> 5\%$ blasts (for patients with less than 5% blasts at baseline only), $\geq 50\%$ increase to $> 10\%$ blasts (for patients with 5-10% blasts at baseline only), $\geq 50\%$ increase to $> 20\%$ blasts (for patients with 10-20% blasts at baseline only), $\geq 50\%$ increase to $> 30\%$ blasts (for patients with 20-30% blasts at baseline only) or any of the following: At least 50% decrement from maximum remission/response in granulocytes or platelets, reduction in Hgb by ≥ 2 g/dL, or New or worsened transfusion dependence not related to study drug toxicity. Or for patients with a CR, Marrow CR, or PR as defined above and subsequently development of one of the following: Return to pretreatment bone marrow blast percentage, decrement of $\geq 50\%$ from maximum remission/response levels in granulocytes or platelets, or reduction in Hgb concentration by ≥ 1.5 g/dL or transfusion dependence.

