14.2.2 Primary Endpoint Analysis

The primary end-point of this phase II study is the correlation biomarkers with overall response in AML/MDS patients to decitabine.

We will correlate the presence of patient specific mutations (especially mutations in *DNMT3A*, *IDH1*, *IDH2*, and *TET2*) with overall response rates. Mutation rates in these genes and in other patient-specific genes will be correlated with overall response and their respective 95% confidence intervals will be provided.

Statistical considerations. The relationship between AML/MDS-associated mutations and the responsiveness to decitabine will be described by contingency tables and assessed using Chi-square test or Fisher's exact test as appropriate. The differentially expressed genes between responders and non-responders will be determined using the significance analysis of microarray (SAM). Multivariate logistic regression will also be fit to adjust the potential confounding effects of other demographic and clinical characteristics. The resultant critical *P* values will be corrected for multiple testing. Since the Bonferroni correction is known to be too conservative, a permutation analysis (e.g., 10,000 random assignments for

responsive status) will be used to derive an empirical critical P value. The new critical p-value is the number of permutation tests which yield a lower p-value than the original test divided by the total number of permutation tests.[61]

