A power analysis was performed using Chi-square test for the association between mutation and response to decitabine. The frequency of *DNMT3A*, *IDH1/2*, and *TET2* mutations in AML and MDS patients are each between 15% and 30% in multiple cohorts.[29-37] **Table 3** shows the minimal detectable differences of response rates between mutant and wild-type cases, assuming an expected overall 45% CR/CRi rate and 80% power. For an average of 20% frequency of a mutated gene, for example, 100 patients will provide 80% power to detect 30% difference at a 2-sided 0.1 alpha error. The purpose of this study is to determine whether any of these mutations result in a clinically significant association that would warrant pre-treatment testing. We believe that a reasonable cut off would be if at least 30% of clinical response could be attributed to the presence of a specific mutation. However, we anticipate that more power could be achieved as we assess patient groups with combined characteristics (e.g. *DNMT3A* mutation or loss of *DNMT3A* expression). In addition, we expect that the majority of the enrolled 125

Table 3. Detectable mutation associated response rates (80% power, $\alpha = 0.05$)

Total N	% of patients with a given mutation	Detectable response difference	Sensitivity of mutation to predict response at minimum detectable response difference*
100	15%	0.40	80%
	20%	0.35	75%
	30%	0.30	67%
	40%	0.27	61%
	50%	0.26	58%

* Assuming the overall response rate (CR/CRi) of 45%

patients can be used in the analysis (since all of our molecular information will be acquired within 30 days of enrollment, we anticipate a drop-out rate of 20% or less).

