14.2.3 Secondary Endpoint Analyses

The overall response rate (CR/CRi/PR) and complete response rate (CR/CRi) will be compared with historical controls[2], and the 95% confidence intervals will be provided.

The rate of patient specific mutation clearance after 10, 28, and 56 days of therapy will be determined using an Illumina based platform. We will compare the rate of mutation clearance between the patients who achieve a CR/CRi after 4 cycles and those who do not. We anticipate that we will identify between 6 and 25 exonic SNVs per case (the range obtained with >200 AML samples sequenced to date with whole genome or exome sequencing), and that the expected 95% confidence interval of the mean variant allele frequency will be $\pm 2.56\%$ and $\pm 1.25\%$,

respectively, if we assume an anticipated standard deviation of 3.2% within the same clone. The change of tumor burden over time and its association with clinical response will be assessed using 2-way ANOVA for repeated measurement data, followed by the ad-hoc multiple comparisons for between-group differences (e.g., responders vs. non-responders) at given time points as well as the between-time differences within each group. The resultant critical P values will also be corrected using permutation analysis for multiple testing.

The percent decrease in bone marrow methylcytosine will be calculated on day 10 ± 1 . We will compare this reduction with previously published data and between the patients who achieve CR/CRi and those who do not. The correlation of peak plasma levels of decitabine with response will be assessed using 2-sample t-test or Mann-Whitney non-parametric rank-sum test as appropriate. The change of total bone marrow DNA methylcytosine from baseline and its association with both steady-state plasma drug levels and response will be assessed using 2-way ANOVA for repeated measurement data, followed by the ad-hoc multiple comparisons for between-group differences (e.g., responders vs. non-responders) and between-time differences. Similar analyses will be performed for the correlation of expression profiles and SNP analysis with pharmacokinetic data.

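### The primary outcome, overall response, has two category lists in the plan, and neither assigns MDS Marrow CR although both include its AML counterpart, CRi

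*Combined protocol and SAP*

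**What the plan says.** Section 2.1 sets the objective: "To determine whether patient-specific mutations correlate with clinical overall response to decitabine in patients with AML or MDS". Section 14.2.2 repeats the term: "The primary end-point of this phase II study is the correlation biomarkers with overall response in AML/MDS patients to decitabine". Neither lists the categories that make a patient a responder.

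Categories appear in two other places, and they differ:

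- The Table 3 footnote in 14.2.2, on which the power rests, reads "Assuming the overall response rate (CR/CRi) of 45" percent.
- Section 14.2.3 reads "The overall response rate (CR/CRi/PR) and complete response rate (CR/CRi) will be compared with historical controls". Here CR/CRi is the complete response rate, and overall response also includes PR.

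Section 9.1 defines CR, CRi and PR for AML. Section 9.2 defines CR, Marrow CR and PR for MDS, with no CRi. CR in MDS has its own rules, for example "Persistent dysplasia does not exclude CR but will be noted". Section 5.1 joins AML patients reaching CRi with the case where "MDS patients achieve a marrow complete response (Marrow CR) as defined in Section 9.0" as one trigger for the same schedule change, and Section 6.3 repeats the pairing.

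Section 1.1 says that AML and MDS will be analysed together. Section 14.2.2 plans a chi-square or Fisher test, a logistic model adjusting for factors it does not name, and a permutation step that reshuffles response status with no restriction by disease. Section 14.2.5 does not list AML versus MDS as a subgroup. The response wording is the same in every protocol version in the combined file.

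**The concern.** The trial exists to sort patients into responders and non-responders and compare mutation carriers across that split. PR patients change sides depending on which section the analyst follows. Marrow CR patients have no stated side, so someone may have to decide after seeing the data.

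If the lists are followed as written, a patient whose marrow clears without count recovery is a responder with AML and a non-responder with MDS. Recorded response in MDS is then lower by construction. In a pooled test this has two effects. Real associations are diluted, because some MDS responders are scored as failures. And a gene that is unequally common in the two diseases picks up part of the artificial gap as an apparent association. The split by CR/CRi used in 14.2.3 for mutation clearance and methylcytosine carries the same gap.

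**Working it through.** **Inputs from the documents (14.2.2, Table 3).** N = 100 evaluable; 45% overall CR/CRi; 20% of patients mutated; difference 0.35 at two-sided alpha 0.05 (table), or 0.30 at two-sided alpha 0.10 (text); 80% power.

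**Formula.** With carrier fraction f and difference d, the rates are p1 = 0.45 + (1 − f)d and p2 = 0.45 − f·d. Power = Φ[(p1 − p2 − z·SE0)/SE1], where SE0 uses the pooled variance and SE1 the separate variances.

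**Step 1: the plan's own figure.** For f = 0.20, d = 0.30, alpha 0.10: p1 = 0.69, p2 = 0.39, n = 20 and 80. SE0 = √(0.45 × 0.55 × (1/20 + 1/80)) = 0.1244 and SE1 = 0.1169. Power = Φ[(0.30 − 1.645 × 0.1244)/0.1169] = 79.3%, which reproduces the stated 80%. For the 20% row of Table 3: p1 = 0.73, p2 = 0.38, SE1 = 0.1131, power = Φ[(0.35 − 1.96 × 0.1244)/0.1131] = 82.6%, with a detectable difference of 0.340.

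**Step 2: PR in or out.** The PR rate is not given. If adding PR raises the overall rate from 45% to an assumed 50–60%, the detectable difference at 20% mutated moves from 0.340 to 0.337–0.321. The change is small. What matters here is the choice of responder set.

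**Step 3: power if Marrow CR is scored as non-response.** Let m be the MDS share of patients and q the share of MDS responders who are in Marrow CR. Neither is in the documents; I take m = 20–50% and q = 20–60%. I also assume that the planned effect holds for the harmonised outcome, that response and gene frequency are equal in the two diseases, and that q is the same in carriers and non-carriers. Every recorded rate is then multiplied by k = 1 − m·q.

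| m | q | k | Recorded overall rate | Recorded difference (true 0.35) | Power, alpha 0.05 | Power, alpha 0.10 (true 0.30) |
|---|---|---|---|---|---|---|
| none misscored | – | 1.00 | 45.0% | 0.350 | 82.6% | 79.3% |
| 20% | 20% | 0.96 | 43.2% | 0.336 | 79.0% | 76.1% |
| 35% | 40% | 0.86 | 38.7% | 0.301 | 69.8% | 68.2% |
| 50% | 60% | 0.70 | 31.5% | 0.245 | 55.7% | 56.2% |

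**Step 4: type I error with no true association.** Use the same m and q, and assume gene frequency 30% in one disease and 15% in the other, the ends of the range that 14.2.2 gives for the named genes. Recorded response is 0.45 in AML and 0.45(1 − q) in MDS. At m = 50%, q = 60%, with 30% in AML and 15% in MDS:

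- MDS recorded rate: 0.45 × 0.40 = 0.18.
- Carrier fraction: 0.5 × 0.30 + 0.5 × 0.15 = 0.225.
- Carrier response: (0.5 × 0.30 × 0.45 + 0.5 × 0.15 × 0.18)/0.225 = 0.360.
- Non-carrier response: (0.5 × 0.70 × 0.45 + 0.5 × 0.85 × 0.18)/0.775 = 0.302.
- Spurious difference: 5.8 points; rejection rate of the unadjusted test 8.8%.

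At the mild end (m = 20%, q = 20%) the difference is 1.1 to 1.5 points and the rejection rate 5.1%. In simulations of related scenarios, a disease-stratified Cochran-Mantel-Haenszel test brought the rate back to 4.8–5.0%.

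**The case against.** The strongest reply is that this is a wording gap, and much of it stands.

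- A reader might infer that both lists consist of AML-only categories. They do not: CR and PR are defined for MDS in 9.2, and only CRi has no MDS entry.
- A reader might infer that the plan declares Marrow CR a non-response. No section says so; it is unassigned. Section 5.2.8 calls patients on six-week cycles CRi or better, although 6.3 opens those cycles to Marrow CR as well. CRi may therefore be loose shorthand for both.
- A reader might treat CRi and Marrow CR as equivalent. The protocol pairs them as a milestone, but the criteria differ. Marrow CR needs at most 5% myeloblasts and a fall of at least half; CRi needs all AML CR criteria except neutrophil or platelet recovery.
- The 14.2.3 sentence concerns a secondary comparison with a phase II study in older AML patients, where AML categories are natural. That is so, but 14.2.2 supplies no list of its own.
- The Table 3 footnote may mean overall in the sense of carriers and non-carriers combined. Even then, the power is for CR/CRi while the named outcome includes PR elsewhere.
- The logistic model could adjust for disease type. It could, but disease type is not named, and the chi-square or Fisher test remains unstratified. Unrestricted permutation does not remove a disease-driven difference.

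A reader might also quote a fixed type I error near 8%. One example giving that figure takes 75 AML and 50 MDS patients, recorded response of 45% and 25%, and carriers at 10% and 30%. The 10% lies below the 15–30% in 14.2.2, and Table 3 plans on 100 patients. With 15% and 30% carriers and 60 AML and 40 MDS patients, the simulated rate is 6.2%. With equal gene frequencies there is no spurious difference.

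**Conclusion.** The point holds in this form: overall response has two category lists, the primary analysis section does not say which applies, and neither list assigns Marrow CR while both include CRi. That conclusion rests on the text alone.

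The size depends on quantities that the documents do not give. Under the assumed ranges, the type I error of the unadjusted test is about 5.1–8.8%, and power at the 20% row is 79.0–55.7% instead of 82.6%. Lost power is the larger risk and needs no imbalance in gene frequency. The conflict over PR matters for who counts as a responder and hardly at all for power. The documents do not support the stronger claim that every gene more common in one disease would show a material false association. Severity: should-fix.

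**What to change.** In 14.2.2, state one responder definition per disease and use it unchanged in Table 3 and 14.2.3. An example is CR, CRi or PR for AML and CR, Marrow CR or PR for MDS, with the version without PR as a sensitivity analysis. If the investigators decide that Marrow CR is not a response, the plan should say so and give the reason. State the planning response rate for the chosen definition.

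Stratify the primary mutation–response test by AML versus MDS, for example with Cochran-Mantel-Haenszel, and permute response status within disease. Name disease type as a covariate in the logistic model. Stratification alone repairs the type I error but does not recover responders scored as failures, so both changes are needed.

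The cost is SAP wording and possibly a restated planning rate. The response categories in Section 9 are already collected, so no new procedure is required.

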We and others have recently used whole genome sequencing to identify recurrent, somatic mutations in AML and MDS patients in four genes that are involved in methylcytosine regulation: *DNMT3A*, *IDH1*, *IDH2*, and *TET2*. [29-37] Collectively, nearly half of all AML/MDS patients have a mutation in one of these four genes. *DNMT3A* mutations are associated with an adverse outcome in AML patients treated with cytotoxic chemotherapy. [35, 38] However, it is not yet clear whether the presence of mutations in one or more of these genes is associated with response or resistance to decitabine.

In this study, we will treat patients with the current state-of-the-art decitabine schedule. [3] We will perform exome sequencing on all patients and correlate response with mutation status, rate of mutation clearance, expression profile, plasma decitabine levels, and DNA

methylcytosine content reduction. This approach will comprehensively assess genomic and pharmacologic parameters that could clinically predict patient response to decitabine.

In this study, we will combine analysis of patients with AML and MDS. Recent genomic analysis has shown that AML and MDS have shared mutations in many of the same genes, shared patterns of mutation acquisition, and shared patterns of mutation evolution.[39, 40] Furthermore, MDS, like AML, presents with clonal hematopoiesis, even when the morphologic blast count is zero.[36] Because this study will identify and track the rate of clearance of patient specific mutations, and because decitabine has been shown to have efficacy in both AML and MDS patients, [2, 3, 16-19, 41-45] combining analysis of AML and MDS patients is reasonable. Asymptomatic MDS patients are excluded because these patients are typically followed with watchful-waiting rather than with chemotherapy.

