1.3 Correlative Studies

All correlative studies will be collected under HRPO# 201011766 (“Tissue Acquisition for Analysis of Genetic Progression Factors in Hematologic Diseases”) that all patients will be concurrently enrolled in. The goals of the correlative studies include:

1. To correlate patient-specific mutations with response to decitabine.
We will perform exome sequencing of each patient’s pre-study bone marrow sample and skin sample. We will determine AML/MDS-associated variants found in the bone marrow, but not skin sample. We will correlate the presence of mutations with response (especially mutations in *DNMT3A*, *IDH1*, *IDH2*, and *TET2*). This study is powered to identify mutations with >80% sensitivity to predict decitabine response if used as a clinical assay.
2. To correlate the velocity and depth of response with response to decitabine.
We will assess tumor burden by allele frequency of patient-specific mutations in bone marrow samples collected pre study, Cycle 1 Day 10±1, Cycle 1 Day 28±4, and Cycle 2 Day 28±4. We will assess mutations in at least 24 recurrently mutated genes (including, but not limited to: *FLT3*, *DNMT3A*, *NPM1*, *TET2*, *WT1*, *IDH1*, *IDH2*, *RUNX1*, *NRAS*, *TP53*, *U2AF1*, *KRAS*, *PHF6*, *MSTP9*, *PTPN11*, *KIT*, *SMC3*, *PRUNE2*, *ETV6*, *CEBPA*, *SMC1A*, *ASXL1*, *STAG2*, *RAD21*) as well as all patient-specific mutations discovered during exome sequencing. The leukemic allele frequency will be measured using the Illumina MySeq or HiSeq platform using DNA capture by gene specific biotinylated-oligonucleotides. Patient bone marrow samples will be assessed pre-study, Cycle 1 Day 10 ± 1, Cycle 1 Day 28 ± 4, and Cycle 2 Day 28 ± 4 and compared with patient specific skin samples (normal control). The velocity of response will be calculated as the natural log rate of patient-specific mutation allele frequency clearance. Depth of response will be defined as the lowest patient-specific mutation

allele frequency in a bone marrow sample. The velocity and depth of tumor response will be correlated to:

- Achievement of clinical CR,
- Time to best response,
- Mutational status,
- Time to disease progression.

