9.3 Guidelines for Evaluation of Disease

Bone marrow biopsy should be performed on Day 28 ± 4 of cycles 1, 2, 4 and 6 for clinical disease assessment. Following Cycle 6, bone marrow biopsies should be performed at the discretion of the treating physician to assess for relapse or progression.

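### Day 28 and Day 56 mutation clearance is compared by a CR/CRi status that the same marrows can establish, so a difference there can arise with no predictive value

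*Combined protocol and SAP*

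**What the plan says.** Section 14.2.3 sets the measurement times: "The rate of patient specific mutation clearance after 10, 28, and 56 days of therapy will be determined using an Illumina based platform". Section 1.3, item 2, names the marrows: "samples collected pre study, Cycle 1 Day 10±1, Cycle 1 Day 28±4, and Cycle 2 Day 28±4". It also defines the measure: "The velocity of response will be calculated as the natural log rate of patient-specific mutation allele frequency clearance". Depth is the lowest allele frequency found in a marrow sample.

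Section 14.2.3 then gives the comparison: "We will compare the rate of mutation clearance between the patients who achieve a CR/CRi after 4 cycles and those who do not". It adds a repeated-measures ANOVA with responder versus non-responder contrasts at given time points. Section 1.3 also correlates velocity and depth with achieving clinical CR.

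For response, section 9.3 says: "Bone marrow biopsy should be performed on Day 28 ± 4 of cycles 1, 2, 4 and 6 for clinical disease assessment". Section 5.2.8 confirms that each of these procedures supplies both the correlative sample and the morphologic assessment. For AML CR, section 9.1 adds: "No duration requirement for this designation".

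On purpose, section 1.1 lists the rate of mutation clearance among the "parameters that could clinically predict patient response to decitabine". Section 2.2 puts the secondary objective as correlation with overall response.

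**The concern.** A predictor has to be observed before the outcome it predicts. Two of the three post-baseline clearance marrows are also response marrows. AML CR needs no confirmation, so a Cycle 1 or Cycle 2 marrow, together with the blood counts, can establish it. For a patient whose response is first documented on one of those marrows, the clearance value and the marrow part of the response call come from one sample. If the response was documented earlier, the clearance value comes after the outcome.

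Sections 1.3 and 14.2.3 set no landmark, do not exclude patients already in CR/CRi, and give no rule for shared samples. The ANOVA contrasts and the correlations of velocity and depth with CR are open to the same problem. Depth is the most exposed, because the lowest allele frequency may come from the remission marrow itself.

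At stake is the first-listed biomarker in the second secondary objective. A Day 28 or Day 56 difference could mean only that marrows scored as remission contain less leukemia, yet be read as evidence that early clearance predicts response.

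**Working it through.** **The plan's own clearance figures.** Half-width = 1.96 × SD/√n with SD 3.2%: 1.96 × 3.2/√6 = 2.56% and 1.96 × 3.2/√25 = 1.25%, as stated. Two-sample t-test power (two-sided 0.05, n = variants per time point):

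- 10% difference, 6 variants: 99.8% at SD 3.2%; 91.2% at SD 4.7%.
- 15% difference, 3 variants: 98.6% at SD 3.2%; 82.8% at SD 4.7%.

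The plan states >99%, 91%, >98% and 82%, so the figures reproduce. They take variants within a patient as the unit, so none of them covers the responder versus non-responder comparison of clearance.

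**Sample overlap.**

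| Marrow | Clearance (1.3, 14.2.3) | Response (9.3) |
|---|---|---|
| Cycle 1 Day 10 | yes | not listed |
| Cycle 1 Day 28 | yes | yes |
| Cycle 2 Day 28 (Day 56) | yes | yes |
| Cycle 4 Day 28 | no | yes |

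**Simulation 1, best response by Cycle 4.** N = 100 with a 45% response rate (the plan's planning values), two-sample t-test at two-sided 0.05, 2,000 runs per setting. At each marrow, clearance = ρ × blast clearance in that marrow + √(1 − ρ²) × independent noise. Nothing carries over between marrows, so early clearance has no predictive value. A patient responds if blast clearance passes a threshold at Cycle 1, 2 or 4, and f is the share of responses first declared at Cycle 1 or 2. Both ρ and f are assumptions. Rejection rates, Day 28 / Day 56:

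| ρ | f = 25% | f = 50% | f = 75% | f = 100% |
|---|---|---|---|---|
| 0 | 5.4 / 4.4% | 4.4 / 6.0% | 6.2 / 5.8% | 5.2 / 4.9% |
| 0.3 | 6.9 / 6.6% | 11.0 / 12.4% | 16.4 / 21.3% | 27.2 / 35.2% |
| 0.5 | 10.0 / 11.0% | 21.6 / 26.6% | 39.3 / 49.6% | 56.9 / 78.3% |
| 0.7 | 14.6 / 15.8% | 37.6 / 45.4% | 66.2 / 79.6% | 86.2 / 97.4% |
| 0.9 | 20.2 / 24.8% | 59.0 / 67.2% | 87.6 / 95.6% | 98.4 / 99.9% |

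Day 10 stays at 4.4–5.6% throughout.

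**The same model, status read on the Cycle 4 marrow only.** Day 28 / Day 56 rejection is 5.2% / 4.8% at ρ = 0.5 and 5.6% / 4.4% at ρ = 0.9, which is nominal. That result depends on nothing carrying over from one marrow to the next.

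**Simulation 2, on the allele-frequency scale.** Assumptions: 45 of 100 patients are responders by chance alone; baseline leukemic fraction 30–90%; allele frequency half the fraction; measurement SD 3.2/√6; remission marrows at 0–10%; other marrows keep 40–110% of baseline; 40% of by-Cycle-2 responses are already present at Day 28. Approximate rejection rates:

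| Reading and setting | Day 28 | Day 56 |
|---|---|---|
| Best response; 50–90% documented by Cycle 2; all patients' allele frequency follows morphology | 59–95% | 99.9–100% |
| Best response; 50–90% by Cycle 2; half follow | 21–51% | 76–99% |
| Best response; 25% by Cycle 2; half follow | 10% | 31% |
| Cycle 4 marrow only; 60–80% of early remissions persist; 50–70% by Cycle 2; 50–100% follow | 8–59% | 22–99.8% |

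On the best-response reading, limiting the test to patients not yet in response at that marrow, and counting only later responses, returns rejection to 4–6%.

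**Responders left at a Day 56 landmark.** 45 × (1 − share documented by Cycle 2): 45 × 0.5 = 22.5; 45 × 0.3 = 13.5; 45 × 0.1 = 4.5.

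**The case against.** The strongest reply is that the plan mostly promises correlation. Section 2.2 asks whether biomarkers correlate with response, and 14.2.3 speaks of association. If responders' Day 28 and Day 56 allele frequencies really are lower, rejecting is the right answer to that question and becomes wrong only when presented as prediction. This stands, and it is why the remedy is largely one of labelling. Section 1.1 nevertheless lists clearance among the parameters meant to predict response, so the label matters.

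Second, the four-cycle phrase can be read as status on the Cycle 4 marrow, which is not a clearance sample. That reading is open, but the text does not choose it. It also leaves the ANOVA contrasts and the section 1.3 correlations untouched, since neither is limited to Cycle 4, and it does not protect against early remissions that persist.

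Third, allele frequency and blast count are different measures. CR also requires blood counts and transfusion independence, and section 1.1 notes that MDS can be clonal with no morphologic blasts. This weakens the coupling by an amount nobody can read from the documents.

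Fourth, Day 10 clearance is already a planned comparison. That is correct, but it is not singled out as the predictive one. One caution applies: Appendix 2, footnote d, also lists the Cycle 1 Day 10 marrow for clinical disease assessment, so the Day 10 analysis should state that it counts responses first documented at Cycle 1 Day 28 or later.

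A reader might infer that a positive result is built into the design. The documents do not support that: with weak coupling or few early responses, rejection stays near nominal.

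**Conclusion.** The point holds in this form: marrows are shared between predictor and outcome, no landmark is set, and a Day 28 or Day 56 difference can arise with no predictive value. The simulated range of about 5% to nearly 100% shows how far the answer depends on ρ and f, or on their equivalents in the second model. It is not an estimate for this trial. Exposure is greatest under best response by Cycle 4 and can remain under the Cycle 4 marrow reading. The planned permutation correction does not address it: the correction deals with multiplicity, whereas this association is genuinely in the data.

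The reach is limited to a secondary analysis. It would be wrong to infer that the primary mutation-response test is compromised, since that test uses mutation status from the pre-study marrow. Clearance to Day 10 is also unaffected. This is an inexpensive clarification worth making, and the trial's main question does not depend on it.

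**What to change.** Amend section 14.2.3 and section 1.3, item 2:

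- **(a)** Define *after 4 cycles*: best response by Cycle 4, or status on the Cycle 4 marrow.
- **(b)** Name clearance from pre-study to Cycle 1 Day 10 as the predictive comparison, for response first documented at Cycle 1 Day 28 or later.
- **(c)** Report the Day 28 and Day 56 contrasts, and depth, against CR/CRi as concurrent association and not as prediction.
- **(d)** As a supporting analysis, repeat Day 28 and Day 56 in patients who have not reached CR/CRi (Marrow CR for MDS) at or before that marrow, counting only later responses.

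The change is to the wording of the analysis plan and uses samples already scheduled. The cost falls on (d): at Day 56, about 22, 14 or 4–5 of 45 responders remain if 50%, 70% or 90% of responses are documented by Cycle 2. At the upper end that comparison is nearly empty, so it can support (b) but not replace it.
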